1.0 SYNOPSIS

This amendment to Protocol #999a seeks:

- 1. to collect longer term safety data during an aggregate of 52 weeks of continuing double blind and open buprenorphine treatment. This extension protocol will be available to subjects continuously receiving buprenorphine who successfully completed the initial study and any current continuations of that study,
- 2. to permit certain modifications to the parent protocol. These modifications will reduce subject burden from participation compared to the parent protocol. Previous studies have indicated these modifications to be safe, and
- 3. to collect information for "directions for use" to be included in labeling language as part of an NDA.

Upon conclusion of the parent protocol and applicable continuation for any given subject, this amendment will permit:

- 1. the study sites to collect and analyze urine specimens for drug screening proposes. These results will be used by the investigators for dose modification and counseling purposes.
- 2. dose modification to the next higher or lower dose. This modification may be made at any time during the course of this amendment. An additional dose of 32 mg will be added to the dosage range to permit escalation from the current highest study dose in the parent protocol.
- 3. continuation of buprenorphine dosing for up to 52 weeks total [i.e., parent, continuation (if any), and extension].
- 4. reduction of clinic attendance to 5 or 6 days per week at the request of study site personnel. Because take home doses will not be permitted, a double dose not to exceed 32 mg will be administered on day 5 or 6 of the clinic schedule.
- 5. reduction of frequency and extensiveness of assessment.

All patients who enroll in this extension will be maintained on buprenorphine in a double blind status until the last eligible patient at all sites has completed 12 additional weeks of dosing under the extension protocol.

In order to provide a comparison group for safety measures included in this study, "scooped" data from methadone patients treated at the individual sites will be gathered during the course of this extension protocol. This information will reflect the number of patients followed at the clinic, the demographic descriptors of those patients, the dose of methadone received, numbers of program drop outs/terminations, and adverse events. It is anticipated that adverse event reporting for the methadone patients may not be as extensive as it is for the study patients. To the extent methadone adverse experience data are available for reporting, they will be used for comparison to the experience of patients participating in this extension amendment. No patient identifiers will be reported with these data; only the aggregate data normally reported to governmental agencies will be utilized for this comparison.

There are several compelling reasons to collect longer term safety data on buprenorphine in opiate addicts:

- 1. the safety data derived from buprenorphine analgesia patients may not be applicable to this population because opiate addicts may require higher buprenorphine doses than used for analgesia and longer duration of dosing compared to analgesia patients;
- 2. opiate abusers often take a variety of other street drugs and prescription medications, increasing chances of unanticipated drug-drug interactions compared to pain patients; and
- 3. many opiate abusers have pre-existing liver disease or other chronic illnesses. Hence prior safety data of buprenorphine in pain patients is not entirely relevant for opiate addicts.

In addition to long term safety data, this protocol amendment permits the gathering of limited self report and observer reported data with regard to the dose modification including the newly added 32 mg dose. This information is not intended as efficacy data, but will be reported in labeling language descriptively characterizing the dosing experience among these patients during the extension amendment.

It is also expected that amending this protocol to provide for extended dosing will enhance retention in the original protocol. It could be expected that compliance will increase because:

- 1. subjects will be less likely to terminate if a regular methadone treatment slot were to become available to them
- 2. subjects who prefer buprenorphine to other opiate-dependence treatment (i.e., naltrexone or methadone), will perceive the opportunity to remain on buprenorphine to be a personal advantage and health benefit.

Attrition due to the above factors, which is not related to the study medication, tends to erode the strength of drug abuse treatment studies.

Only modifications to the parent protocol will be explicitly identified in this amendment. Unless specified, methods identified in the parent protocol will maintain in this amendment.

This amendment will begin at each participating site as quickly as possible after obtaining IRB approval. In order to permit complete development of this extension amendment, a continuation amendment at some, but not all sites has been filed. Where implemented, the continuation amendment included all procedures from the parent protocol in order to obtain expedited approval. Certain data not specified in this present extension amendment were gathered during the continuation phase of this study. Those data not identified in this extension amendment will be retained for archival purposes at the individual sites, but will not be analyzed as part of the NDA document.

Should a given site wish to continue to gather data relevant to the parent protocol but not specified for the extension amendment, they may do so, including the use of case report forms developed for the parent protocol. If this choice is made, the data will be stored at the site for archival purposes, but will not be reported for inclusion in the data analysis phase of this amendment.

INTRODUCTION

Background: Preclinical

See Parent Protocol

Background: Clinical

See Parent Protocol

Rationale/Disease Review

See parent protocol

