- 1. *Serum plasma levels of buprenorphine* will be collected at weeks 2 and 8. The sample will be drawn 24 hours after the previous dose and before administration of the next buprenorphine dose. The plasma will be frozen and sent to a central laboratory for analysis.
- 2. *Missed doses* Each site will keep records (Coordinators Weekly Report Form 12 and Dose Administration Record Form 19) documenting the administration of each dose. The number of missed doses will be computed from these records.
- 3. Adverse experiences will be evaluated at screening (Medical History and Status Form 06) and weekly thereafter (Adverse Events Form 16). The questions to elicit this information are open ended. The signs, symptoms or life-events need not necessarily be caused by buprenorphine. The study sites must report within 24 hours serious adverse experiences (i.e., death, experience resulting in permanent disability or hospitalization) to the sponsor (NIDA), the IRB, and the

Clinical Coordinating Center. (The sponsor will report the reaction to FDA.) Form 17 (Serious Adverse Event Form) must be completed for all serious adverse experiences.

- 4. A complete physical examination will be done at baseline and termination and recorded on the medical monitoring form. An abbreviated physical examination (Form 09) will be done monthly. More frequent medical evaluations may be conducted as clinically indicated.
- 5. *The amount of psychosocial treatment* provided patients will be recorded weekly on Form 14 Psychosocial Services Received. This measure is to monitor comparability of groups on the amount of psychosocial services received.

Schedule of Data Collection

Instruments	Screen	Week of Study															
		1	2	3	4	5	6	7	8	9	10	11	12	13	14	15	16
Form 01 - Background Information	X																
Form 02 - Drug Use History	X																
Form 03 - DSM-III-R Criteria for Diagnosis																	
of Opiate Dependence	X																
Form 04 - Global Rating (Staff)	X				X				X				X				X
Form 05 - Global Rating (Patient)	X				X				X				X				X
Form 06 - Medical History and Status	X																
Form 07 - Craving Scale	X																
Form 08 - Laboratory Report	X		X		X				X				X				X
Form 09 - Physical Exam	X				X				X				X				X
Form 10 - Electrocardiogram	X				X												X
Form 11 - Study Admission	X																
Form 12 - Coordinators Weekly Report		X	X	X	X	X	X	X	X	X	X	X	X	X	X	X	X
Form 13 - Weekly Self-Report of Drug Use																	

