8.0 CRITERIA FOR RESPONSE

Measures and Measuring Instruments:

Those variables used primarily to evaluate safety are:

- 1. Adverse experiences will be evaluated at the time of entry into the extension protocol and weekly thereafter as in the parent protocol.
- 2. Laboratory data CBC, UA, SMA-12 will be collected every twelve weeks and EKGs will be taken 24 weeks after the completion of the parent protocol and at the termination.

Those variables which will be used primarily to provide descriptive analyses of method modifications (dose adjustments, dosing schedule, doubled weekend doses) for inclusion in "directions for use" label language are:

- 1. Self reported frequency of illicit drug and ethanol use will be obtained every week.
- 2. Abbreviated self report including reports of opiate side effects and withdrawal symptoms.

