Type of Report I=Anticipated adverse	Relatedness 1=Study drug related 2=Probably study	Severity 1=Mild 2=Moderate	Acti 1=None 2=Prescription or 0	on Taken	Aransy ramina		Outcom	sequelac
event 2 = Unanticipated adverse event 3 = Intercurrent illness 4 = Withdrawal symptom †5 = Development of clinically significant abnormal lab value	drug related 3=Possibly study drug related 4=Unrelated to study drug	lization requi g therapy and equired	zation required *3=Resulted in chronic condition, severe and/or permanent disability quired *4=Deceased the dy due to effect *3=Resulted in chronic condition, severe and/or permanent disability *4=Deceased the dy due to effect					
Considering the patient's lescribe, in the investiga associated information l	tor's own words, eacl	ns 1, 2, and 3 of Adverse Even	above and any oth t, Intercurrent Illu	er pertinen sess or Clir	nt informat nically Sign	ion (i.e., l uificant Ab	ab results normal l	s, etc.), please Lab Value and
Nature of Illnoor Abnormal	ess, Event	Date of Onset (mo day yr)	Date of Resolution (mo day yr)	I. Type of Report	II. Related- ness	III. Severity	IV. Action Taken	V. Outcome
a.							Ш	
ь.				Ш				
c.								
d.						Ш	Ш	
е.						Ш	Ш	
f								
May require completion of								
4. Is a Serious Adverse Event Form (Form 07) required? 1 Yes 2 No								
FORM COMPLETED E	BY							
NVESTIGATOR'S SIG	NATURE			· · · · ·	Date _			
/A Form 10-20923(NR)p November 1991			48					

FORM 07 - S	ERIOUS ADV	ERSE	EVENT FORM	М					
AUDY NO. 999a EXT	CENTER NO.		PATIENT NO.						
	I. ADVERSE	EVENT	STUDY WEEK NO.						
PATIENT INITIALS	2-4. EVENT ONSET Month: Day:	Year:	5. Age: (yrs)						
SEX	7. HEIGHT (in)		8. WEIGHT (lb)						
A. PROVIDE A NARRATIVE DESCRIPTION OF EVENT:									
		ACTION TA	/EN						
B. GREATEST C. STUDY DRUG SEVERITY 1 = Mild 2 = Moderate 3 = Severe 2 = Probable 3 = Severe D. DOSE CHANGE 0 = No Change 0 = No Change 1 = Reduced 0 = No Treatment 1 = Resolved 2 = Temp. Dc'd 1 = Outpatient Tx 2 = Ongoing 3 = Perm. Dc'd 2 = Hospitalization 3 = Died									
G. If Died, List Primary Cause of Death:									
Relevant Tests/Laboratory Data	:								
II. SU	SPECT DRUG(s)	INFORM	IATION						
. Suspect Drug(s) (Give Trade/G	eneric Name(s), Manufa	acturer):							
2. Daily Dose:	3. Route of Administrati	on: 14	14. Dates of Administration: (from/to)						
5. Indication(s) for Use:	16	. Duration of	Administration:						
III. CON	III. CONCOMITANT DRUG(s) AND HISTORY								

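### The extension's methadone adverse event comparison mixes unequal reporting with completer selection, so a difference in either direction could not be attributed to buprenorphine

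*Combined protocol and SAP*

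**What the plan says.** The extension Synopsis (section 1.0) gathers data on methadone patients treated at the sites "In order to provide a comparison group for safety measures included in this study". The items are patient numbers, demographics, methadone dose, drop-outs or terminations, and adverse events.

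- **Source of the methadone events.** There are no patient identifiers, and "only the aggregate data normally reported to governmental agencies will be utilized for this comparison".
- **Completeness.** "It is anticipated that adverse event reporting for the methadone patients may not be as extensive as it is for the study patients". The size of the shortfall is not given.
- **Use.** The next sentence still commits to the comparison: "To the extent methadone adverse experience data are available for reporting, they will be used for comparison".
- **Buprenorphine events.** Section 8.0 states: "Adverse experiences will be evaluated at the time of entry into the extension protocol and weekly thereafter as in the parent protocol". The data collection schedule in Appendix B has Form 06 (Adverse Events) at each of weeks 1 to 36. The form opens with scripted questions and then records severity (from mild upwards), relatedness, action taken and outcome. Its event types include "3 = Intercurrent illness 4 = Withdrawal symptom" and clinically significant abnormal laboratory values. The parent protocol (Other Measures, item 3) adds: "The signs, symptoms or life-events need not necessarily be caused by buprenorphine".
- **Who enters the extension.** Section 5.2 admits only patients who completed the parent study, and any continuation, without a break.
- **Analysis.** Section 9.0 does not mention methadone. Its stated comparisons are with parent-protocol data.

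**The concern.** The two sides of the comparison are collected in different ways. On buprenorphine, events are actively sought every week, whatever their cause and down to mild severity. For methadone, the plan states no form, question schedule, grading or common definition, and takes only what reaches routine aggregate returns. A difference in event counts would be expected from the method of collection alone, even if true risks were identical.

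The plan foresees the gap but does not act on it. No section restricts the comparison to events that both sources would record, names a denominator, or says how the gap limits interpretation.

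Longer-term safety is the first aim of the extension, the data are intended for an NDA, and methadone is the only comparator that is not buprenorphine. A reader of the report would naturally look to this comparison to put the buprenorphine event rate in context, and it cannot serve that purpose.

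**Working it through.** The documents give no event rate, capture fraction, sample size, test or margin for the methadone comparison, so there is no plan figure to reproduce. The check is in two steps, and all values of f and k below are assumptions.

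**Inputs from the documents**
- Buprenorphine: events elicited at entry and weekly (section 8.0; Form 06 in 36 weekly columns, Appendix B). Total treatment is 52 weeks, of which 16 are the parent study: 52 − 16 = 36.
- Methadone: aggregate returns, expected to be less extensive (section 1.0).
- Buprenorphine patients are uninterrupted completers (section 5.2). Section 7.1 (Drug Discontinuation Criteria) describes toxicity in such patients as remote. No matching selection is stated for the methadone patients.

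**Step 1: ascertainment alone.** Take weekly questioning as the reference (capture = 1). Let f be the fraction of such events that the methadone returns contain. With equal true risks,

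apparent ratio (buprenorphine / methadone) = 1 / f

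- f = 0.9: 1 / 0.9 = 1.11
- f = 0.75: 1 / 0.75 = 1.33
- f = 0.5: 1 / 0.5 = 2.00
- f = 0.25: 1 / 0.25 = 4.00

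**Step 2: add completer selection.** Let k be the true risk in the extension completers relative to the clinic methadone patients. Selecting patients who tolerated the drug for the whole parent study would be expected to push k below 1. Then

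apparent ratio = k / f

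| f | k = 0.3 | k = 0.5 | k = 0.7 | k = 1.0 |
|---|---|---|---|---|
| 0.9 | 0.33 | 0.56 | 0.78 | 1.11 |
| 0.75 | 0.40 | 0.67 | 0.93 | 1.33 |
| 0.5 | 0.60 | 1.00 | 1.40 | 2.00 |
| 0.25 | 1.20 | 2.00 | 2.80 | 4.00 |

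The ratio falls below 1 whenever k is smaller than f. For example, 0.7 / 0.75 = 0.93, while 0.7 / 0.5 = 1.40. The same k gives opposite conclusions at two plausible capture fractions. The documents supply neither quantity, so the sign of the net bias cannot be determined.

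**What the defect does not reach.** The section 9.0 comparisons set extension data against parent-protocol data. The parent protocol also collected adverse events weekly (Other Measures, item 3; Form 16 in all 16 weekly columns of its schedule). Those comparisons are free of this particular ascertainment gap.

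**The case against.** The strongest reply is that the plan is candid and modest. It discloses the reporting gap, uses the methadone data only as far as they exist, sets no test or significance level for them, and leaves methadone out of both the objectives (section 3.0) and the statistics (section 9.0). On this view the methadone data are background context. The methadone drop-out and termination counts, moreover, do not depend on weekly questioning. Nor do the documents describe how the clinics collect adverse events, so the capture shortfall is anticipated but not known.

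Much of this stands, and it rules out three stronger readings that a reader might be tempted to make.

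- **That the comparison must make buprenorphine look less safe.** Ascertainment alone pushes that way, but completer selection pushes against it and neither size is given.
- **That a stated false-positive rate follows.** Any such percentage needs a test, an event risk and group sizes, and the plan states none of these for methadone. Aggregate returns may even count events rather than patients, in which case a comparison of proportions could not be made.
- **That the extension's whole safety evaluation merely measures reporting effort.** The comparisons in section 9.0 are with parent-protocol data, and reporting effort is one of several influences on the methadone comparison.

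The reply does not remove the core point. Disclosing a gap is not the same as limiting what may be concluded from it. The Synopsis calls these patients a comparison group for safety and commits to comparing their adverse events, with no restriction.

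**Conclusion.** The point holds in limited form. As written, the methadone adverse event comparison is confounded by unequal ascertainment, which the plan itself anticipates, and by restriction of the buprenorphine side to uninterrupted completers. Assignment between the two drugs is also not random. A difference in either direction could not be attributed to buprenorphine.

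The ascertainment component alone would multiply the apparent buprenorphine-to-methadone ratio by 1.11 to 2.0 for assumed capture fractions of 0.9 to 0.5. This takes weekly questioning as the reference and true risks as equal. The size and sign of the net bias are unknown.

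This is a secondary, descriptive comparison, so the defect does not threaten the parent trial's efficacy conclusions or the analyses set out in section 9.0. It should still be corrected, because it concerns the only non-buprenorphine safety reference in an extension whose first aim is safety.

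**What to change.** Amend the methadone paragraph of the extension Synopsis (section 1.0), and repeat the change in section 9.0, where methadone is now absent:

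1. Limit the methadone adverse event comparison to events that both sources record under the same definition: deaths, and hospitalizations if the sites' aggregate returns include them.
2. Express these against the number of patients followed, which the plan already collects. Use patient-months only if the returns allow it.
3. State that the comparison is descriptive, and that it is limited by completer selection in the extension and by non-random assignment. Restricting the event types narrows the ascertainment gap but leaves these two problems in place.
4. List all other methadone adverse events only, with no test, rate ratio or comparative safety statement against the extension.

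The cost is a minor amendment with the usual sponsor and IRB approvals, plus a check of what the returns contain. No comparative statement could be made on non-serious events, but these data could not support one in any case.

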3.0 OBJECTIVES

The objectives of this study are:

- 1. to provide an opportunity to collect longer term safety data on buprenorphine;
- 2. to permit certain modifications to the parent protocol in dosing, schedule, and assessment to reduce subject burden from protocol participation;
- 3. to increase subject incentive to complete successfully the parent protocol;
- 4. to give subjects who did well on buprenorphine continued access to the treatment medication for a total of 52 weeks; and,
- 5. to perform a descriptive analysis of the experience associated with modifications in methods; see "2." above for inclusion in "directions for use" language in an NDA for buprenorphine.

4.0 STUDY DESIGN

This extension amendment provides drug dosing to all patients who successfully complete the original protocol 999a and any applicable continuation of that parent protocol for an aggregate total of 52 weeks. Compared to the parent protocol and applicable continuations, this amendment permits:

- the study sites to collect and analyze urine specimens for drug screening purposes. These results will be used by the investigators for dose modification and counseling purposes.
- 2. dose modification to the next higher or lower dose. This modification may be made at any time during the course of this amendment. An additional dose of 32 mg will be added to the dosage range to permit escalation from the current highest study dose (16 mg) in the parent protocol. There are no limits to the number of dose modifications that can be made during the extension (no more than one dose change per day). At the time of enrollment or any time thereafter patients in the extension protocol and their treating physician may choose to double or to halve the individual's dose. These modifications may occur as

frequently as deemed clinically indicated, but in no instance will the dose increase beyond 32 mg/day or decrease to less than 1 mg/day.

- 3. reduction of clinic attendance to 5 or 6 days per week depending upon the decision of study site personnel. Because take home doses will not be permitted, a double dose not to exceed 32 mg will be administered on clinic day 5 or 6.
- 4. reduction of frequency and extensiveness of assessment.

Previous studies indicate that doses up to 32 mg/day have been safely tolerated even in normal volunteers (Walsh, et al, 1992a). Prior work has also indicated that withdrawal symptoms from fixed doses of 8 mg. of buprenorphine appear after 48-72 hours (Fudala, et al, 1990). Hence doubling doses is expected to provide coverage from withdrawal symptoms during the weekend dosing schedule.

All patients who enroll in this extension will be maintained on buprenorphine in a double blind status until the last eligible patient at all sites has completed 12 additional weeks of dosing after the parent protocol or has been terminated. At that time the study can be opened for an investigator to know the dose of buprenorphine being administered to any given patient.

Assessment frequency is modified and reduced as reflected in the Schedule of Data Collection (see Appendix B - Study Forms). During the extension, the sites will have access to the urine drug screen results to enable the staff to better deal with the addicts' behaviors. Urine drug screening should be performed by the individual sites to provide information for clinical decisions regarding dose modification and protocol eligibility. Urine drug screen results will not be used as an efficacy measure; therefore results will not be reported to nor collected by the sponsor.

Data analysis in the extension study will assess the safety variables by dose, dose modification, and presence of other drug use.

Initiation of this study shall begin after local site approval of the amendment. Once in effect, this extension amendment supersedes any continuation amendments in place at that site.

